Study protocol**Material and Methods****1. Patient**

The Consolidated Standards of Reporting Trials (CONSORT) statement guidelines were followed in this single-center, prospective, parallel group, assessor-blinded, randomized controlled trial. All procedures were approved by the institutional review board of Police general hospital.

Patients who were diagnosed isolated closed fracture of distal end radius at Police General Hospital, Bangkok, Thailand between October 2021 and February 2023 were divided into the conventional group and the MIPO group at recruitment, using a computer-generated randomization program from www.randomizer.org. Patients were informed about the treatment options during a pre-interviewing session, and all eligible patients gave their written informed consent before the randomization and initialization of the allocated treatment. When patients arrived in the operating room, randomization took place using sealed envelopes containing assigned numbers. These envelopes were in the operating room and remained unopened until the patient's arrival. Neither the patient nor the attending physicians were informed about the randomization process. The orthopedic surgeon who assessed patient eligibility was not involved in randomization, thereby securing allocation concealment.

Inclusion criteria:

-We included those diagnosed with isolated closed fractures of the distal end radius requiring surgery,

-aged 18 years and older.

The Exclusion criteria were:

(1) Patients with bone fractures lasting more than 21 days

(2) open fractures

- (3) articular multifragmentary comminuted fractures of the distal radius categorized as AO/OTA 2R3C3
- (4) not suitable to undergo volar approach surgery
- (5) individuals with combined carpal fractures or dislocation
- (6) ulna fractures
- (7) associated injuries
- (8) a history of previous wrist surgery
- (9) diabetes mellitus
- (10) chronic wrist inflammation
- (11) wrist bone deformities
- (12) the use of anticoagulation drugs
- (13) uncooperative behavior
- (14) those refusing to participate in the research

2. Methods

According to the WALANT solution in our institute (Jaroenporn et al., 2022), the steps for preparing the solution are as follows (Figure 2A). Firstly, 40 ml of 1% Lidocaine with adrenaline (1:100,000) and 10 ml of 0.5% Marcaine are added to the solution. Marcaine, a long-acting local anesthetic, helps prolong the duration of pain relief. Additionally, 40 ml of Normal Saline Solution (NSS) is included; NSS acts as a diluent and ensures the appropriate volume of the anesthetic solution. Finally, 4 ml of 7.5% NaHCO₃ (sodium bicarbonate) is added to balance the acid-base pH. By following these steps, a total solution volume of 94 ml is prepared.

All patients underwent volar locking plate fixation under WALANT. First, the periosteum of the radius is infiltrated at three different points: proximal, middle, and distal (radial styloid), with each point receiving 10 ml of anesthesia. This ensures that the circumferential periosteum of the radius bone is adequately anesthetized. Next, a subcutaneous infiltration along the volar skin incision of 10 ml is injected (Figure 2B). After a 30-minute period of allowing the anesthesia to take effect

Operative Procedure for MIPO:

The patient, under WALANT, was in the supine position on the surgical table. A minimal 2 cm skin incision was made on the volar side of the wrist, proximal to the wrist crease 2 cm. The Trans flexor carpi radialis approach (Trans FCR) was performed, and the surgical plane was dissected using curved scissors to increase exposure. To mobilize and protect the flexor carpi radialis (FCR) and flexor pollicis longus (FPL) ulnarily, a self-retractor was employed. Care was taken to avoid damaging the radial artery on the radial side and the palmar cutaneous branch of the median nerve on the ulnar side. The distal aspect of the pronator quadratus muscle was elevated using a periosteal elevator. A partial transverse cut was made in the pronator quadratus muscle at the distal end to approach the fracture site. Closed reduction and temporary fixation with K-wires were used to assist in the reduction. The alignment was checked under fluoroscopy. The DePuy Synthes VA-LCP Two-Column Distal Radius Plates 2.4, volar, narrow, with 6 head holes and a width of 19.5 mm (Synthes USA Products, LLC), were utilized in the procedure. These plates were chosen for their minimal width, allowing easy insertion through a small incision. One cortical screw was inserted into an elongate hole, followed by the insertion of 4 distal locking screws. An additional proximal vertical mini incision of 1 cm was made for fixation with 2 proximal locking screws. No drain was inserted, and cast immobilization was not required.

Post-operation:

Adhering to post-operative protocols, no drain was inserted, and cast immobilization was unnecessary. Immediate encouragement of active finger and wrist motion was provided after the operation. Both groups were administered pain medication for 7 days, including Tramadol (50 mg), 1 tablet three times daily; Naproxen (250 mg), 1 tablet twice daily; and Tolperisone (50 mg), 1 tablet three times daily. In cases where the patient's Visual Analog Scale (VAS) pain score exceeded 5, a 3 mg IV dose of morphine was administered as needed by the patient.

As part of their early post-operative rehabilitation, patients were instructed in the six-pack exercise and wrist range of motion (ROM) exercises.

3. Evaluation

The data collector, an orthopedic resident unaware of the surgical technique used, obtained information. Neither the collector nor the patients observed the surgical incision.

[figure not shown]
The primary outcome was measured using the pain visual analogue scale (VAS). Regarding the pain VAS, a score of 0 indicated no pain, and a score of 10 indicated the worst imaginable pain. The pain VAS score was recorded in the morning first 7 day then in the 2nd, 6th, 10th, 14th, and 24th weeks after surgery.

Patients attended outpatient department (OPD) follow-up appointments in the 2nd, 6th, 10th, 14th, and 24th weeks after surgery. The Quick Disabilities of the Arm, Shoulder, and Hand (Quick DASH) score indicated a functional outcome. The patient's satisfaction, along with the cosmetic score (rating the scar's appearance on a scale of 0 to 5, with 5 being excellent),. Hand grip strength was measured as a percentage of the strength in the other hand using a baseline hydraulic hand dynamometer with a JAMAR device (lbs force) from Sammons Preston, Inc., Bolingbrook, IL 60440-4989, in a 90 degree raised and extended arm position. The patient squeezed the dynamometer three times, and the highest score was recorded. Pinch strength was assessed by raising the patient's arm in front of them and bending it at a 90-degree angle, testing with a JAMAR Hydraulic Pinch Gauge. Three pinches on the device provided the highest score.

[figure not shown]
4 Statistical Analysis

IBM SPSS Statistics 27.0 was utilized for statistical analysis. Results were expressed as the mean \pm standard deviation. Statistically significant differences were determined based on $P < 0.05$ and the 95% confidence interval (CI). The Fisher's exact test was used to evaluate baseline characteristics including sex, fracture side, cause, AO/OTA type. The paired t-test was used to evaluate the age, incision length, VAS pain score, Quick DASH, functional outcomes (grip, pinch strength, range of motion), operative time, Aesthetics, Satisfaction and radiographic parameters. All subjects were analyzed and none of the subjects were lost to follow-up.

CONSORT diagram

[figure not shown]
Method

Data collection process

1) Pain Visual Analog Score

Pain Rating Scale – Wong-Baker FACES™ & Visual Analogue Scale (VAS)

Source:

Pain assessment in children undergoing venipuncture: The Wong-Baker faces scale versus skin conductance fluctuations - Scientific Figure on ResearchGate. Available from: https://www.researchgate.net/figure/Wong-Baker-Faces-TM-Pain-Rating-Scale-Reproduced-with-Permission-of-the-Wong-Baker-Faces_fig1_236604762 [accessed 12 Feb, 2020]

This work by Department of Pharmacology and Pharmacy, HKU is licensed under a [Creative Commons Attribution-NonCommercial 3.0 Hong Kong License](https://creativecommons.org/licenses/by-nc/3.0/). Last updated Feb 2020.

Postoperative day	date	Pain VAS
0		
1		
2		
3		
4		
5		
6		
7		

2) QuickDASH form

QuickDASH

Please rate your ability to do the following activities in the last week by circling the number below the appropriate response.

	NO DIFFICULTY	MILD DIFFICULTY	MODERATE DIFFICULTY	SEVERE DIFFICULTY	UNABLE
1. Open a tight or new jar.	1	2	3	4	5
2. Do heavy household chores (e.g., wash walls, floors).	1	2	3	4	5
3. Carry a shopping bag or briefcase.	1	2	3	4	5
4. Wash your back.	1	2	3	4	5
5. Use a knife to cut food.	1	2	3	4	5
6. Recreational activities in which you take some force or impact through your arm, shoulder or hand (e.g., golf, hammering, tennis, etc.).	1	2	3	4	5

	NOT AT ALL	SLIGHTLY	MODERATELY	QUITE A BIT	EXTREMELY
7. During the past week, to what extent has your arm, shoulder or hand problem interfered with your normal social activities with family, friends, neighbours or groups?	1	2	3	4	5

	NOT LIMITED AT ALL	SLIGHTLY LIMITED	MODERATELY LIMITED	VERY LIMITED	UNABLE
8. During the past week, were you limited in your work or other regular daily activities as a result of your arm, shoulder or hand problem?	1	2	3	4	5

	NONE	MILD	MODERATE	SEVERE	EXTREME
9. Arm, shoulder or hand pain.	1	2	3	4	5
10. Tingling (pins and needles) in your arm, shoulder or hand.	1	2	3	4	5

	NO DIFFICULTY	MILD DIFFICULTY	MODERATE DIFFICULTY	SEVERE DIFFICULTY	SO MUCH DIFFICULTY THAT I CAN'T SLEEP
11. During the past week, how much difficulty have you had sleeping because of the pain in your arm, shoulder or hand? (circle number)	1	2	3	4	5

QuickDASH DISABILITY/SYMPOTM SCORE = $\left(\frac{\text{sum of } n \text{ responses}}{n} \right) - 1 \times 25$, where n is equal to the number of completed responses.

A QuickDASH score may not be calculated if there is greater than 1 missing item.

3) Table data collection

	MIPO	Conventional	p-value
Mean age, (SD); range			
Sex			
female			
male			
fracture side			
Dominant Hand			
Non-dominant Hand			
Cause			
fall			
road traffic accident			
sports			
AO/OTA 23			
A2			
A3			
B3			
C1			
C2			

	wk 2	wk 6	wk 10	wk 14	wk 24
(lbs)	F/U 1	F/U 2	F/U 3	F/U 4	F/U 5
Grip strength Fx					
Grip strength normal					
Pinch strength Fx					
Pinch strength normal					
ROM Fx					
Flexion					
Extension					
Supination					
Pronation					
Radial deviation					
Ulnar deviation					
Pain (0-10)					
QuickDASH					
Wound size (mm)					
Cosmetic score					
Satisfy score					

	MIPO	Conventional	P-value
Pain score			
Q-DASH score			
Grip strength			
Subjective cosmetic			
Satisfaction			

Volar tilt	MIPO	Conventional	P-value
Initial			
Immediate post operation			
Final			

Radial inclination	MIPO	Conventional	P-value
Initial			
Immediate post operation			
Final			

Ulnar variance	MIPO	Conventional	P-value
Initial			
Immediate post operation			
Final			

patient	Pain (0-10)												mo	Q-DASH (0-100)						
	(no #)	Pre	D1	D2	D3	D4	D5	D6	D7	wk2	wk6	wk10	wk14	wk24	(mg)	Pre	wk2	wk6	wk10	wk14

patient	X-ray									Cos	Sat	Hand grip						
	RI			UV			VT					Hand grip						
	Pre	Post	F/U	Pre	Post	F/U	Pre	Post	F/U			wk2	wk6	wk10	wk14	wk24

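### Pain VAS is primary at 12 post-operative readings, but the plan does not say which reading, summary or multiplicity rule decides the result

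*Combined protocol and SAP*

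**What the plan says.** Section 3 (Evaluation) names the primary variable: "The primary outcome was measured using the pain visual analogue scale (VAS". The next lines define the 0 to 10 scale and give the schedule: "The pain VAS score was recorded in the morning first 7 day then in the 2nd, 6th, 10th, 14th, and 24th weeks after surgery".

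Section 4 (Statistical Analysis) puts pain in a long list of variables that share one method: "The paired t-test was used to evaluate the age, incision length, VAS pain score, Quick DASH", followed by the remaining functional, operative and radiographic measures. The significance threshold is 0.05. The section gives no primary day or week, average, area under the curve, change score, repeated-measures model or adjustment for several tests.

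Three forms under *Data collection process* bear on the question:

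- The pain diary, headed "Postoperative day", has rows for days 0 to 7.
- The per-patient grid has pain columns Pre, D1 to D7, and weeks 2, 6, 10, 14 and 24.
- The between-arm results table has single rows for pain score, Q-DASH score and grip strength. Each has one P-value cell and no day or week.

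**The concern.** A variable measured 12 times is not yet an endpoint. The primary comparison needs a stated time point, a stated summary of the readings, or a stated rule for combining 12 tests. Without one, a reader cannot tell which result the primary conclusion rests on. The pain result could be settled after the data are seen: an early day, the last visit, an average, or whichever reading is significant. If the content may be chosen by its P-value, the error rate of the primary claim is above the nominal 5%.

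The two arms may also differ in early pain and not at week 24, or the reverse. The choice then affects what the trial is said to have shown, as well as the error rate.

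**Working it through.** **1. Count the readings.** The schedule in section 3 gives 7 daily readings plus 5 visits (weeks 2, 6, 10, 14, 24): 7 + 5 = 12. The post-operative columns of the per-patient grid agree. The grid adds a Pre column (13 columns in all), and the diary adds a day 0 row.

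**2. Look for a rule that selects among them.** Section 4 has none. The follow-up table with week columns lists pain, but it is a collection form without arm or P-value columns. The between-arm table has an unlabelled pain row. The radiographic tables are split by time, with rows such as "Immediate post operation", but the Q-DASH and grip rows are as unlabelled as the pain row. The between-arm table therefore does not settle the question.

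**3. No design figure to reproduce.** The documents give no sample size, standard deviation, effect size or correlation between readings. The rest is an illustration on stated assumptions.

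**4. Size of the open choice.** Assumptions: no true difference; each reading tested between arms at two-sided 0.05 by a valid test (sidedness is not stated in the plan); any one significant reading may be claimed.

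- Independent readings: 1 − 0.95^12 = 0.460.
- Common correlation ρ, with c = 1.96: 1 − ∫ [Φ((c − √ρ·z)/√(1−ρ)) − Φ((−c − √ρ·z)/√(1−ρ))]^12 φ(z) dz.

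| Assumed ρ | Chance of at least one false positive in 12 |
|---|---|
| 0 | 0.460 |
| 0.3 | 0.397 |
| 0.5 | 0.319 |
| 0.7 | 0.232 |
| 0.8 | 0.186 |
| 0.9 | 0.135 |

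A simulation of 20,000 null trials with two-sample t-tests and an assumed 30 patients per arm gave 0.318, 0.236 and 0.135 at ρ = 0.5, 0.7 and 0.9, so the integral is adequate at that size. If correlation instead decays with the distance between readings (AR(1) in reading order), the chance is 0.213, 0.345 and 0.409 at lag-one correlations of 0.9, 0.7 and 0.5.

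**5. Compare with a defined endpoint.** One pre-specified summary per patient is one test. In the same simulation the mean of the 12 readings gave 0.049 to 0.053. If all 12 readings were kept as co-equal, a Bonferroni rule would need 0.05/12 = 0.0042 for each.

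**The case against.** The strongest reply is that the documents nowhere say that 12 tests were run or that any one of them would count as success. That is right. The percentages depend on an any-reading rule and on assumed correlations, and zero correlation is implausible for repeated pain scores in one patient. A narrower choice inflates the error less. Taking the best of three candidates picked here for illustration (day 1 to 7 mean, day 1, week 24) gives 8%, 10% and 11% at ρ = 0.9, 0.7 and 0.5, and the documents name none of the three. The absence of a defined primary comparison needs none of these assumptions, so that part of the concern stands.

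A reader might infer more in three places, and the documents do not support it:

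- *That a favourable reading was selected.* The text is in the past tense and reports complete follow-up ("All subjects were analyzed and none of the subjects were lost to follow-up"), but nothing shows how the pain result was chosen.
- *That the single pain row shows one comparison was intended.* Other repeated measures have the same unlabelled row. The table may be a generic layout, filled once per visit.
- *That the forms can be dated to before the trial.* The line "Last updated Feb 2020" follows the licence notice of a reproduced third-party pain scale. It dates that sheet, not the trial's diary or tables.

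The Pre column does not contradict a schedule that lists readings after surgery, and day 0 may be that same reading or an unused row. This is a matter for clarification only. Figures are missing from the text, but no surviving analysis sentence points to a figure that defines the endpoint.

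**Conclusion.** The concern holds as a gap in definition: the plan names a primary variable but no primary comparison. Under an any-significant-reading rule the false-positive chance would be about 13% to 32% at common correlations of 0.9 to 0.5, against a nominal 5%. The 46% figure applies only to independent readings and should not be quoted as the expected size. The calculation describes what the plan leaves open and is no evidence about what was done.

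It also takes each single test to be valid at 5%. The plan names a paired t-test in a parallel-group trial without defining a pair, so that is itself an assumption; the choice of test is a separate matter.

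**What to change.** 1. Search for a dated document, written before the data were seen, that names the time point or summary. If there is one, cite it and use it.
2. If there is none, name one between-arm primary test and label it post hoc. One workable example is ANCOVA of each patient's day 1 to day 7 mean VAS on arm, two-sided 0.05, with pre-operative VAS as covariate if the Pre column was actually filled. If it was not, compare the mean between arms without adjustment. The documents do not favour this summary over another; what matters is that there is one.
3. Label the pain row of the results table accordingly. Report every other time point as secondary, with estimates and 95% confidence intervals.
4. Report morphine use by arm beside the primary result. The post-operation section allows morphine as needed when VAS exceeds 5, and both groups receive pain medication for 7 days, so scores in that window partly reflect analgesia. The per-patient grid has a column headed mo (mg), read here as morphine.
5. State whether the day 0 diary row is the Pre value, and align the schedule, the diary and the grid.

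The cost is some wording, a search for dated evidence, and one model on data already collected. Without such evidence the primary result is post hoc: readers gain transparency but no guaranteed 5% error, because that guarantee needs a choice made before the data were seen. An isolated significant day can no longer be claimed as the primary result.

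### Grip is measured as a percentage of the other hand, but the recorded dominance of the fractured hand is left out of the grip analysis, so available precision is given up

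*Combined protocol and SAP*

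**What the plan says.** Under 3. Evaluation, "Hand grip strength was measured as a percentage of the strength in the other hand". Under 4 Statistical Analysis, one method, a paired t-test, is named for a list of continuous variables that includes "functional outcomes (grip, pinch strength, range of motion". No covariate, stratified analysis or regression model appears anywhere in the plan.

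The baseline table under 3) Table data collection splits fracture side into dominant hand and "Non-dominant Hand". The only use made of it is a comparison of the arms at baseline: "The Fisher's exact test was used to evaluate baseline characteristics including sex, fracture side, cause, AO/OTA type".

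The visit form in the same section records grip in lbs for the fractured hand and, in the row "Grip strength normal", for the other hand, at weeks 2, 6, 10, 14 and 24. The summary table that follows has one grip row, with neither a unit nor a visit.

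Under 1. Patient, allocation was made "using a computer-generated randomization program from www.randomizer.org". No stratification by dominance is described. The primary outcome is pain on the visual analogue scale.

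**The concern.** A ratio of the fractured hand to the other hand changes meaning with the side of the fracture. In a dominant-side fracture the weaker hand is the denominator and the percentage is pushed up. In a non-dominant-side fracture the stronger hand is the denominator and the percentage is pushed down. Two patients who have recovered the same fraction of their own strength then score differently for a reason unrelated to surgery. Dominance is thus a predictor built into the outcome definition whenever the hands differ in strength.

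Leaving it out puts that spread into the error term and widens the confidence interval for grip. If the arms happen to differ in their share of dominant-side fractures, the estimated grip difference also carries that imbalance. Fisher's test can describe an imbalance but does nothing to the grip estimate, and in a small trial a non-significant result does not show that the imbalance is harmless.

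**Working it through.** The plan gives no sample size, SD, dominance effect or expected grip value, so there is no figure of its own to reproduce. Everything below rests on assumptions.

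**Assumed inputs.** Dominant hand stronger by a factor k = 1.05, 1.10 or 1.15; recovery to r = 70% of the hand's own strength; SD within each dominance group s = 15 or 20 percentage points; half of fractures on the dominant side (p = 0.5); n = 20 to 30 per arm.

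**Step 1: gap by dominance.** A dominant-side fracture reads r × k and a non-dominant-side fracture r / k, so the gap is D = r(k − 1/k).

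- k = 1.05: 70 × (1.0500 − 0.9524) = 6.8 points
- k = 1.10: 70 × (1.1000 − 0.9091) = 13.4 points
- k = 1.15: 70 × (1.1500 − 0.8696) = 19.6 points

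With 80% recovery the gaps are 7.8, 15.3 and 22.4 points.

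**Step 2: variance explained and gain.** The unadjusted variance is s² + p(1 − p)D² = s² + 0.25D². The share due to dominance is v = 0.25D² / (0.25D² + s²). Adjustment narrows the confidence interval by 1 − √(1 − v), which is worth v / (1 − v) more patients.

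| k | D | s | share v | CI narrower by | equivalent extra patients |
|---|---|---|---|---|---|
| 1.05 | 6.8 | 20 | 2.8% | 1.4% | 2.9% |
| 1.05 | 6.8 | 15 | 4.9% | 2.5% | 5.2% |
| 1.10 | 13.4 | 20 | 10.0% | 5.2% | 11% |
| 1.10 | 13.4 | 15 | 16.6% | 8.7% | 20% |
| 1.15 | 19.6 | 20 | 19.4% | 10.2% | 24% |
| 1.15 | 19.6 | 15 | 30.0% | 16.3% | 43% |

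If k = 1, then D = 0 and every entry is zero.

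**Step 3: chance imbalance.** The SD of the difference between arms in the proportion of dominant-side fractures is √(2p(1 − p)/n) = √(0.5/n), which is 0.158 at n = 20 and 0.129 at n = 30. A one-SD imbalance moves the grip difference by D√(0.5/n): from 6.8 × 0.129 = 0.9 points to 19.6 × 0.158 = 3.1 points. By simulation, the two proportions differ by 20 percentage points or more with probability 0.27 at n = 20 and 0.16 at n = 30.

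**Step 4: the shift against the standard error.** The unadjusted standard error is √(2(s² + 0.25D²)/n). Dividing the one-SD shift by it gives 0.5D/√(s² + 0.25D²) = √v. This is 0.17 to 0.55 standard errors over the whole range, and 0.32 to 0.41 at k = 1.10.

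**Step 5: type I error.** An unadjusted independent two-sample t-test was simulated with D = 10, s = 15 and no treatment effect, 20,000 trials for each n. It rejected in 0.0496 of trials at n = 20 and 0.0490 at n = 30 per arm. These figures are for a two-sample test, not for the paired test that the plan names.

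**The case against.** The strongest reply is that randomisation already deals with dominance. A reader might infer from the mechanism that the unadjusted result is biased, or that an uneven split would pass as a treatment effect more often than the 5% level allows. The documents do not support that reading. Allocation is random, so the expected imbalance is zero, and the standard error of a valid two-sample comparison already includes the variation due to dominance; the simulated error rates agree. What remains is lost precision, and an estimate in the one realised trial that has not been corrected for whatever imbalance occurred.

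A second reply is that the gain may be small. With 30 per arm, s = 15 and k = 1.10, the 95% half-width falls only from about 8.5 to 7.8 points. Power for an assumed 10-point difference with 30 per arm and s = 15 is 72%, 69% or 58% unadjusted for gaps of 5, 10 or 20 points, against 73% adjusted. Only the largest gap makes a marked difference. The formula also gives every patient the same strength ratio and assumes equal recovery on both sides. This stands as a limit on size.

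Third, a reader might take it as settled that grip is analysed as a percentage. The plan says that it is measured so, but the visit form records lbs and the summary table gives no unit. The percentage scale is the likely reading, but it is inferred, and the mechanism above depends on it.

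Fourth, age, sex and AO/OTA type are also recorded and could be argued for as covariates. That is fair. Dominance differs in that its link to the outcome follows from how the percentage is formed.

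**Conclusion.** The point holds as a minor matter of efficiency. The plan expresses grip relative to the other hand, records whether the fractured hand is dominant, and does not use that in the grip analysis. On the percentage scale, a valid unadjusted comparison would be unbiased with correct type I error, but less precise than the collected data allow, and it would leave any chance imbalance in the estimate.

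The size cannot be taken from the documents. It runs from nothing, if the hands are equally strong, to about 30% of the variance under the largest assumed gap and the smaller SD. Pain is the primary outcome, so the trial's main conclusion is not affected.

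**What to change.** State the scale on which grip is analysed. For grip percentage, and for pinch if it is expressed in the same way, replace the paired t-test, which does not fit two independent arms, with a between-arm linear model containing arm and fracture side (dominant or non-dominant). Name the visit for the comparison, for example week 24 as the last, or include all five visits in a repeated-measures model. Report the adjusted difference with its 95% confidence interval, and do not rely on the baseline Fisher's test to deal with imbalance.

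The statistical section is written in the past tense. If outcome data have already been seen, show the adjusted result beside the unadjusted one and label it as added later.

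The cost is a short addition to the plan, one binary covariate that is already collected, and one degree of freedom. The named software can fit the model.

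### Pinch strength, unlike grip, is not defined relative to the uninjured hand although both hands are recorded; read as written, it is compared unnormalised and loses precision

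*Combined protocol and SAP*

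**What the plan says.** Section 3 (Evaluation) describes the two strength outcomes one after the other. For grip: "Hand grip strength was measured as a percentage of the strength in the other hand". For pinch it gives the arm position and the gauge, then "Three pinches on the device provided the highest score". The other hand is not mentioned for pinch.

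The follow-up form under 3) Table data collection, headed in lbs, has rows "Pinch strength Fx" and "Pinch strength normal" with columns for weeks 2, 6, 10, 14 and 24. Grip has the same pair of rows.

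Section 4 (Statistical Analysis) sends "functional outcomes (grip, pinch strength, range of motion" to one t-test. It does not say which pinch quantity is tested and names no covariate. The summary results table has a grip row but no pinch row, and the per-patient listing has columns for hand grip only.

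**The concern.** Eligibility is any adult aged 18 or over, of either sex, so absolute pinch force depends on how strong the patient is as well as on how far the hand has recovered. The form has no pre-injury or pre-operative pinch, which leaves the uninjured hand as the only within-patient reference. The plan collects that reference at every clinic visit and states no use for it.

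Two things are at stake. The pinch comparison would be noisier than it needs to be. And two outcomes listed side by side would answer different questions: grip, the share of the patient's own strength regained; pinch, the force in lbs. Because the tested variable is not named, the choice between lbs and percentage could also be made after the data are seen.

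**Working it through.** **What the documents supply.** They give the best-of-three rule for pinch, the percentage definition for grip, both hands' pinch at five visits, a significance level of 0.05 and a randomised parallel-group design. They give no sample size, power, effect size, SD or between-hand correlation, so there is no planned figure to reproduce. Everything numerical below is an illustration on assumed inputs.

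**Model.** Fractured-hand pinch = uninjured-hand pinch × recovery ratio, the two factors independent. CVn is the between-patient CV of uninjured pinch (assumed 0.15 to 0.35). CVr is the CV of the recovery ratio (assumed 0.10 to 0.30).

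- Raw reading: CVraw² = CVn² + CVr² + CVn²·CVr²
- Percentage of other hand: CV² = CVr²
- Share of raw relative variance due to between-patient strength = CVn² / CVraw²
- Variance factor, raw over percentage = CVraw² / CVr²
- n per arm for a 10% relative difference (two-sided 0.05, 80% power, 1:1, all assumed) = 2 × (1.96 + 0.84)² × CV² / 0.10²

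Mid case, CVn 0.25 and CVr 0.20: CVraw² = 0.0625 + 0.0400 + 0.0025 = 0.105. Share = 0.0625 / 0.105 = 0.60. Factor = 0.105 / 0.04 = 2.62.

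| CVn | CVr | CVraw² | Share from strength | Factor | n/arm raw | n/arm % |
|---|---|---|---|---|---|---|
| 0.15 | 0.30 | 0.1145 | 0.20 | 1.27 | 180 | 142 |
| 0.15 | 0.10 | 0.0327 | 0.69 | 3.27 | 52 | 16 |
| 0.25 | 0.20 | 0.1050 | 0.60 | 2.62 | 165 | 63 |
| 0.35 | 0.30 | 0.2235 | 0.55 | 2.48 | 351 | 142 |
| 0.35 | 0.10 | 0.1337 | 0.92 | 13.4 | 210 | 16 |

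The factor equals 1 + CVn² + CVn²/CVr², so under this model it always exceeds 1. The direction is built in; only the size varies.

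**With measurement error.** Adding 5% error in the uninjured hand, with CVn 0.20 or 0.35 and a recovery SD of 0.12 or 0.15, the percentage-to-raw ratio of relative variance is 0.32 to 0.69 at 50% mean recovery, 0.19 to 0.52 at 75% and 0.14 to 0.44 at 90%.

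**Covariate instead of percentage.** With between-hand correlation ρ, adjusting for uninjured-hand pinch multiplies the variance by 1 − ρ²: 0.91 at ρ = 0.3, 0.75 at 0.5, 0.51 at 0.7 and 0.19 at 0.9. Apart from one degree of freedom this does not lose precision. A percentage is a difference on the log scale. If the two hands have equal log SDs, its factor is 2(1 − ρ): 1.4, 1.0, 0.6 and 0.2 at the same correlations. In that setting the percentage gains only above ρ = 0.5.

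**Validity.** I simulated 20,000 null trials with an assumed 30 per arm, mean uninjured pinch 15 lbs and mean recovery 0.8, using an unpaired t-test on raw readings. The rejection rate was 0.050 (CVn 0.25, CVr 0.20) and 0.051 (CVn 0.35, CVr 0.10). The mean between-arm difference was 0.02 lbs and 0.00 lbs.

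**The case against.** The strongest reply is that no sentence says the raw reading is what is compared. The form lays out pinch exactly as it lays out grip, in lbs for both hands, and grip is then defined as a percentage; the authors may have meant the same for pinch. This stands in part: the raw comparison is the natural reading, not an explicit statement. It does not remove the point, because the intended percentage is written nowhere, and one sentence settles either reading.

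A reader might also infer that differences in sex and body size swamp recovery, or that most of the information in pinch is thrown away. The documents do not support this. They give no variance or correlation, body size appears nowhere in them, and under the assumed inputs the share due to between-patient strength can be as low as 20%.

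A reader might further infer that a chance imbalance in sex or age makes the raw comparison invalid. It does not: allocation is random, and the error rate already allows for such imbalance. How large an imbalance is likely depends on the sample size, which is not stated, and not on the trial having one centre.

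Two further objections stand. The model ignores hand dominance, which adds noise to a percentage of the other hand and so reduces the gain. And pinch is peripheral: the primary outcome is pain VAS, and the results table has no pinch row.

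**Conclusion.** The point holds as a minor one. Followed as written, the plan compares pinch unnormalised, which is less precise than using the uninjured-hand value it already collects and is on a different scale from grip. The consequence is lost precision on a non-primary outcome, without bias or type I error inflation.

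The size is not known. The range of about 20% to 92% of raw relative variance, or a variance factor of 1.27 to 13.4, rests wholly on the assumed CVs, on independence of strength and recovery ratio, and on no dominance effect. It should not be quoted as a property of this trial.

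The paired t-test that section 4 names for a parallel-group comparison is a separate matter; the working above uses an unpaired comparison.

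**What to change.** In sections 3 and 4, name the pinch variable by one of two routes:

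- **Percentage, matching grip:** highest fractured-hand pinch divided by highest uninjured-hand pinch at the same visit, times 100, compared between arms.
- **Lbs with a covariate:** fractured-hand pinch in lbs, with uninjured-hand pinch as a covariate in a between-group model. This is the safer choice for precision if the correlation between hands turns out modest.

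In either case account for whether the dominant hand was fractured, which the baseline table already records, and show raw lbs descriptively.

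The cost is a sentence in each section; both readings are already on the form. Section 4 is in the past tense and reports that no subject was lost to follow-up, so results may already be known. If they have been seen, label the analysis as post hoc.
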